An essential part of ovarian stimulation involves concomitant treatment with GnRH analogues to prevent premature luteinisation and ovulation,² which can be achieved via two different approaches: pituitary desensitisation with prolonged daily administration of a GnRH agonist or instant blockade of the pituitary luteinising hormone (LH) secretion with a GnRH antagonist.^{3,4,5} Both treatments are effective in preventing premature LH surges^{4,6,7} and comparable in respect of clinical outcomes, such as number of oocytes retrieved and live birth rates.^{5,8} Nonetheless GnRH analogues differ in their safety profile,^{9,10} GnRH agonist treatment being associated with adverse drug reactions related to hypoestrogenism and with higher incidence of OHSS compared with GnRH antagonist treatment, especially in predicted normal to high responders.^{5,8,11}

Differently from the algorithmic dosing of FE 999049, which is based on each subject's serum AMH concentration and body weight, the starting dose in conventional dosing of rFSH is commonly based on age, previous IVF outcomes, and markers of ovarian reserve such as antral follicle counts and circulating AMH, follicle-stimulating hormone (FSH), and estradiol concentrations.^{12,13} A starting dose of 150 or 225 IU rFSH is applied in women with anticipated normal ovarian response, 150 IU being applied in women of younger age and expected to have a robust response, and 225 IU being applied in women of older age or in women expected to have a less robust response.^{14,15} The dose is fixed for the initial days of stimulation, followed by the possibility for subsequent dose adjustments.^{14,16}

Previous trials comparing efficacy and safety of a GnRH antagonist protocol with a long GnRH agonist protocol using rFSH derived from Chinese hamster ovary cell lines in conventional dosing have consistently indicated that the cohort of recruited follicles is slightly smaller with the GnRH antagonist protocol. A difference in oocytes of -1.0 (95% confidence interval [CI]: -1.8; -0.2) was observed in the largest randomised controlled trial⁷ which is in agreement with the difference of -1.1 (95% CI: -1.5; -0.6) in a Cochrane review including data from 27 randomised controlled trials.¹⁷

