This trial is designed to demonstrate non-inferiority of FE 999049 vs. GONAL-F with respect to the number of oocytes retrieved. The non-inferiority margin has been set to 3.00 oocytes, as this margin is regarded to be appropriate for demonstrating the efficacy of FE 999049 treatment in a conventional dosing regimen with a long GnRH agonist protocol. The margin of 3.00 oocytes is in line with the regulatory precedence in Europe for rFSH biosimilars,²¹ and is also a common clinical standard for clinical trials in China demonstrating equivalence between rFSH drug and comparator, e.g. GONAL-F to obtain regulatory approval from the National Medical Products Administration (NMPA).^{22,23,24} Furthermore, the mean number of oocytes retrieved with placebo (i.e. without stimulation) would be approximately 1, and the expected mean number of oocytes retrieved expected with GONAL-F (active control drug) will be approximately 10. Therefore, the efficacy difference between the active control and placebo would be approximately 9, implying that the M1 (defined in the regulatory guideline for clinical non-inferiority trials in China)²⁵ is considerably larger than 3.00. A successful non-inferiority result will therefore both ensure that the effect of FE 999049 is better than placebo and clinically equivalent to GONAL-F, according to regulatory precedence for rFSH biosimilars in Europe and China.^{22,23,24,26,27} Selection of endpoints is further discussed in Section 3.5.2.

Strict criteria have been incorporated in the design of this comparative trial to properly assess the effect of the interventions on treatment outcome. In general, standardisation of criteria, timing of assessments, procedures and interventions have to a great extent been incorporated in the design of this trial to minimise variation.^{28,29,30}

For safety reasons, only subjects with serum AMH concentrations of ≤ 35 pmol/L at screening are eligible for randomisation to treatment and treatment is limited by maximum doses of 20 μ g FE 999049 and 300 IU GONAL-F for a maximum of 20 days. Additional safety measures include cycle cancellation for subjects with ≥ 25 follicles with a diameter ≥ 12 mm or for safety concerns, as judged by the investigator, and transfer cancellation for subjects with retrieval of ≥ 20 oocytes.

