In the current trial, the choice of starting dose level (10 µg FE 999049 / 150 IU GONAL-F or 15 µg FE 999049 / 225 IU GONAL-F) is based on the investigator's clinical judgement. The distribution of starting doses in the trial population will thereby reflect the distribution of starting doses used in clinical practice. After the first 5 days with stimulation at a fixed dose, the dose may be increased or decreased based on the subject's ovarian response by 5 µg FE999049 or 75 IU GONAL-F which are considered doses of similar magnitude based on the extrapolation described above. Dose

adjustments may be implemented not more frequently than once every 2 days. This possibility for a gradual increase in dose and a maximum dose of 20 µg/day FE 999049 or 300 IU/day GONAL-F for a maximum duration of 20 days constitutes a safe approach for the subjects. The starting dose level of GONAL-F is in line with labelling recommendations.²⁰

The doses of overall treatment regimens for the GnRH agonist, hCG, and progesterone products are in line with the recommendations in the respective products' labelling for the indication of ART and/or standard clinical practice.

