9 STATISTICAL METHODS

9.1 Determination of Sample Size

In a previous trial (000145) comparing individualised dosing of FE 999049 with GONAL-F in a GnRH antagonist protocol, the standard deviation for number of oocytes retrieved in subjects from China receiving a starting dose of 150 IU of GONAL-F was 7.5. Assuming the standard deviation in this trial to be 7.5, and assuming the treatments to be equally effective for the primary endpoint (number of oocytes retrieved), a sample size of 133 subjects per treatment group will give 90% power to demonstrate non-inferiority of FE 999049 vs. GONAL-F. This is based on a non-inferiority margin of 3.00 oocytes, a one-sided 2.5% significance level, and was calculated using the normal approximation. A total of 300 subjects will be randomised in the trial to ensure at least 90% power also for the analysis of the per-protocol analysis set.

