9.3 Protocol Deviations

Major protocol deviations, such as significant non-compliance or other serious unforeseen deviations deemed to invalidate the data for the primary endpoint, will lead to exclusion of data from the per-protocol (PP) analysis set. Data will not be excluded from the PP analysis set in case of minor protocol deviations or protocol deviations not affecting the primary endpoint. The list of major protocol deviations includes, but is not limited to:

- Unblinding of assessor
- Non-compliance with IMP for two or more days
- The hCG for triggering of final follicular maturation was incorrectly administered, resulting in no oocytes retrieved

The rating of protocol deviations in ‘minor’ and ‘major’ will be decided by the Ferring clinical team on the basis of a blinded review of data before declaration of clean file and lock of database. If the blinded review identifies serious unforeseen deviations deemed to impact the primary endpoint, these will also be rated as major deviations.

The list of major protocol deviations will be detailed and documented in the clean file document prior to database release.

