9.6 Statistical Analysis

9.6.1 General Considerations

Non-inferiority comparison for the primary endpoint will be performed for both the FAS and the PP analysis set. Other efficacy analyses will be performed for the FAS only. All descriptions of safety data (including the secondary endpoint on OHSS) will be based on the safety analysis set.

Missing data will, in general, not be imputed. For subjects without oocyte retrieval, the number of oocytes, fertilised oocytes, and embryos will be regarded as zero. For pregnancy endpoints, lack of data will be interpreted as a negative pregnancy, unless a subsequent pregnancy endpoint is confirmed to be positive. Missing endocrine values of stimulation day 1 will, when used as covariate, be imputed by the mean of all non-missing values for this visit.

All statistical analyses will be detailed in a Statistical Analysis Plan which will be issued as a separate document and finalised before FPFV.

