9.6.2 Primary Endpoint

The primary endpoint, number of oocytes retrieved, will be compared between FE 999049 and GONAL-F using a negative binomial model with treatment and dose level (10 µg/150 IU or 15 µg/225 IU) as factors. The absolute treatment difference in number of oocytes retrieved and the associated two-sided 95% confidence interval will be derived from the model estimates using the delta method. Non-inferiority will be considered confirmed if the lower limit of the 95% confidence interval for the difference between FE 999049 and GONAL-F is greater or equal than -3.00.

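### Does Section 9.6.2 leave the primary non-inferiority test open by not stating the dose-level mix at which the absolute oocyte difference is computed?

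*Combined protocol and SAP*

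**What the plan says.** Section 9.6.2 and the synopsis specify a negative binomial model with two factors, treatment and dose level (10 µg/150 IU or 15 µg/225 IU). On turning the model into the tested quantity, 9.6.2 names the delta method and says: "The absolute treatment difference in number of oocytes retrieved and the associated two-sided 95% confidence interval will be derived from the model estimates". Non-inferiority is shown if the lower limit is at or above -3.00. No weights for the dose levels and no covariance estimator are named.

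Other sections bear on the point:

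- Section 1.1 describes the higher starting dose as "225 IU being applied in women of older age or in women expected to have a less robust response". The same sentence places both doses among women expected to respond normally.
- Section 3.5.4 leaves the starting dose to the investigator: "The distribution of starting doses in the trial population will thereby reflect the distribution of starting doses used in clinical practice".
- Section 3.5.1 supports the margin with a single overall figure: "expected mean number of oocytes retrieved expected with GONAL-F (active control drug) will be approximately 10".
- Section 9.6.1 says: "All statistical analyses will be detailed in a Statistical Analysis Plan which will be issued as a separate document", and goes on to require that it be final before the first patient's first visit. That SAP was not available for this review.
- Section 9.6.1 also fixes the handling of non-retrieval: "For subjects without oocyte retrieval, the number of oocytes, fertilised oocytes, and embryos will be regarded as zero". Section 9.3 removes from the per-protocol set cases where the trigger was "incorrectly administered, resulting in no oocytes retrieved".

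**The concern.** With the usual log link and no interaction, the model estimates one treatment ratio. The absolute difference at a dose level is that ratio minus one, times the GONAL-F mean there, so it is larger where the mean is larger. A single overall difference therefore needs a rule for combining the two levels. Two rules fit the wording: predict each woman's count at her own dose level and average over the trial's subjects, or evaluate the linear predictor with the levels weighted equally, as least-squares means often do.

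Section 1.1 suggests a lower mean at the higher starting dose, and Section 3.5.4 lets the split fall where it will. If both departures are marked, the two rules give different lower limits, and that limit is the whole decision rule. One fitted model could then pass under one rule and fail under the other.

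A lesser worry is that scoring non-retrieval as zero adds zeros that the model does not expect, so the choice between a model-based and a sandwich standard error might matter.

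**Working it through.** **The plan's own figure.** Inputs from Section 9.1: margin 3.00, SD 7.5, true difference 0, one-sided 2.5%, 90% power. n per arm = 2 × (7.5/3)² × (1.960 + 1.282)² = 12.5 × 10.51 = 131.3, so 132 against the stated 133. Power is 90.4% at 133 and 93.4% at 150. The sample size stands. Its SD is from one dose level only ("the standard deviation for number of oocytes retrieved in subjects from China receiving a starting dose of 150 IU of GONAL-F was 7.5").

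**How far the two rules differ.** Let r be the high-to-low dose-level mean ratio and p the share starting low. The subject-average difference is proportional to p + (1-p)r, and the equal log-scale version to √r. Their ratio is √r / (p + (1-p)r). The documents give neither r nor p, so the ranges below are assumptions. The entries show the equal-weight difference relative to the subject average.

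| r | p = 20% | 40% | 60% | 80% |
|---|---|---|---|---|
| 0.67 | +11.2% | +2.1% | -5.7% | -12.4% |
| 0.8 | +6.5% | +1.6% | -2.8% | -6.8% |
| 0.9 | +3.1% | +0.9% | -1.2% | -3.2% |
| 1.0 | 0 | 0 | 0 | 0 |

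**One fit under both rules.** Assume p = 0.8, r = 0.8 and a treatment ratio of 0.85, with 150 per arm and no added zeros. Take an overall GONAL-F mean of 10 (Section 3.5.1) and SD 7.5.

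- Low-level mean = 10 / (0.8 + 0.2 × 0.8) = 10.42. High-level mean = 8.33.
- Dispersion: the variance of the level means is 0.8 × 10.42² + 0.2 × 8.33² - 100 = 0.69, so k = (56.25 - 10 - 0.69) / 100.69 = 0.452.
- The expected information sums μ/(1 + kμ) over subjects. The delta method is then applied to each rule.
- Subject average: 10 × (0.85 - 1) = -1.50, SE 0.802, lower limit -1.50 - 1.96 × 0.802 = -3.07. This fails.
- Equal log-scale weights: √(10.42 × 8.33) × (0.85 - 1) = -1.40, SE 0.749, lower limit -1.40 - 1.96 × 0.749 = -2.87. This passes.

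**How wide the zone of disagreement is.** In this set-up the verdicts differ only for observed ratios of about 0.835 to 0.858, that is, subject-average differences of 10 × (0.835 - 1) = -1.65 to 10 × (0.858 - 1) = -1.42. At 60% starting low the zone is about 0.848 to 0.857.

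**How often the verdicts differ (simulation).**

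- At no true difference, which is the design assumption in Section 9.1: 4-6% of trials with r = 0.67 and 20% or 80% starting low.
- At a true difference of -1, with 20/60/80% low: 14/7/16% (r = 0.67), 8/4/9% (0.8), 4/2/5% (0.9). At r = 1.0 it is still 3/1/3%, because the estimated means differ by chance.
- With a half-and-half split and r = 0.67: 0.5-2%.

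**Error rates depend on the target.** At a true subject-average difference of -3 and r = 0.67, equal weighting declares non-inferiority in 0.9/1.9/4.3/8.8% of trials at 20/40/60/80% low. Averaging over subjects gives 2.3-2.6% in every cell examined. In the 8.8% cell, however, the true equal-weight difference is -3 × (1 - 0.124) = -2.63, which lies inside the margin. Measured against its own target, that is not a false claim.

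**Covariance estimator** (60% low, r = 0.8, 150 per arm). At 5% added zeros the mean model SE is 0.906 against an empirical 0.857, about 6% too wide. At 10% it is 0.974 against 0.861, about 13% too wide. Power is 92.0% and 89.9%, and one-sided error 2.2% and 1.5%. A sandwich estimator gives power of about 94% but error of 2.7-2.9%, rising to 3.1% at an assumed 140 per arm. At 140 the model-based power is 90.3% and 87.5%.

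**The case for a change.** The strongest case for a change is that the omission is certain in the text, that it touches the only success criterion, and that equal weighting is a familiar software default that the sentence permits. If most women start low, equal weighting shrinks the difference towards zero. If most start high, it costs power (88% against 94% at r = 0.67, 20% low, no true difference). A result near the margin is just where one wants no room for choice, and a sentence would cost nothing.

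Part of this stands. Section 9.6.2 alone does not identify the tested number, and the arithmetic above is right. What does not stand is the step to a defect. The weighting is not left for after the data are seen: Section 9.6.1 commits to detailing all analyses in an SAP finished before the first patient's first visit. Calling equal weighting inflated presupposes the subject average as the target, which is a reasonable choice but not one that 9.6.2 makes. The documents name no software, so the default is hypothetical. Nor do they say how far apart the dose-level means will be. The weaker responders get the higher dose, doses may be adjusted from day 6, and cycles cancelled for excessive response count as zero. All of these could bring the means together.

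**Conclusion.** No change to the plan is needed. This is a detail that the protocol delegates to its SAP and that analysts would fill sensibly. Randomisation is 1:1 within dose level, Section 3.5.4 intends the dose mix to reflect practice, and Section 3.5.1 argues the margin from one overall mean. Together these make the trial's observed mix the natural reading. Equal weighting would be a different but legitimate summary.

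The choice can change the verdict only when the dose-level means differ, the split is far from half and half, and the result lies close to the margin. With means a third apart and a 20:80 split, the two rules disagree in about 4-6% of trials at no true difference and 14-16% at -1. With means within 10% of each other, the figure at -1 is at most about 5%, of which about 3 points remain even when the means are equal. All these figures rest on assumed splits and means.

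The covariance point is a trade-off with no clear gain. The ordinary model-based standard error protects against a false claim, and power stays at about 90-92% with 150 per arm at 5-10% added zeros. The sandwich recovers a little power at the price of slightly more than 2.5% one-sided error. The main uncertainty is that the separate SAP could not be read, so whether it states the weighting is unknown.

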9.6.3 Secondary Endpoints

Number of Follicles

Total number of follicles, and number of follicles ≥ 10 mm, ≥ 12 mm, ≥ 15 mm and ≥ 17 mm, on stimulation day 6 and at end-of-stimulation will (in separate analyses) be compared between FE 999049 and GONAL-F using the same negative binomial regression model as used for the primary endpoint.

Serum Concentrations of Estradiol and Progesterone

Serum concentrations of estradiol and progesterone on stimulation day 6 and at end-of-stimulation will (in separate analyses) be compared between FE 999049 and GONAL-F using analysis of covariance (ANCOVA) models with treatment and dose level as factors and with the serum concentration on stimulation day 1 as a covariate. Multiplicative models will be used, i.e. the serum concentrations will be log-transformed before analysis. The results of the analyses will be back-transformed and presented as estimated geometric means and mean treatment ratios. Values below the lower limit of quantification (LLOQ) will be estimated with LLOQ/2. Potential values above the upper limit of quantification (ULOQ) will be included as ULOQ.

Number of Fertilised Oocytes and Fertilisation Rate

Number of Fertilised oocytes will be compared between FE 999049 and GONAL-F using the same negative binomial regression model as used for the primary endpoint. The fertilisation rate (number of fertilised oocytes/number of oocytes) will be described for subjects with at least one oocyte retrieved.

Number of Embryos

Number of embryos and good-quality embryos will be compared between FE 999049 and GONAL-F using the same negative binomial regression model as used for the primary endpoint.

Total Gonadotropin Dose and Number of Stimulation Days

Total gonadotropin dose will be summarized by treatment and dose level. Number of stimulation days will be compared between FE 999049 and GONAL-F using an analysis of variance model with treatment and dose level as factors.

Pregnancy Endpoints (Positive β hCG rate, Clinical Pregnancy Rate, Vital Pregnancy Rate, and Ongoing Pregnancy Rate)

Pregnancy endpoints will be compared between FE 999049 and GONAL-F using a logistic regression model with treatment and dose level as factors. The results in terms of odds for pregnancy will be converted into proportions, difference in proportions, and a 95% confidence interval for difference in proportions using the delta method.

Implantation Rate and Ongoing Implantation Rate

Implantation rates will be described separately for subjects with single and multiple embryo transfer.

Early OHSS, Late OHSS, and Total OHSS

Occurrences of early OHSS, late OHSS, and total OHSS will be evaluated using descriptive statistics.

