6.5 Stimulation

6.5.1 Stimulation Day 1

Stimulation day 1 visit takes place after downregulation is confirmed. The following must take place before randomisation to treatment:

- Ensure that the subject is still eligible for participation in the trial
- Check those inclusion and exclusion criteria that were not possible during screening
- Urine pregnancy test – must be negative
- Blood collection for central laboratory analysis of estradiol and progesterone
- Transvaginal ultrasound of uterus and ovaries (endometrial thickness, ovarian volume, number and size of follicles). If a cyst ≥ 10 mm is observed (functional or not), it should be punctured before treatment is initiated.^a If the cyst was present at the screening visit, it should have been recorded on the medical history form. If the cyst presented between screening and stimulation day 1, it should be recorded on the adverse event form.

^a Treatment can be initiated the same day. If puncture is not possible, the subject is not to be considered eligible for participation in the trial.

If the subject fulfils all inclusion and exclusion criteria, she will proceed to:

- Assessment of appropriate starting dose level (i.e. 10 µg FE 999049 / 150 IU GONAL-F or 15 µg FE 999049 / 225 IU GONAL-F) and allocation to the corresponding stratum.
- Randomisation to treatment (i.e. FE 999049 or GONAL-F) and assignment to the lowest available subject number within site and stratum.

Once the above has been completed, the following must be performed by the trial medication delegate. Care must be taken to ensure blinding of the investigator and other assessors.

- Dispense IMP according to randomisation and instruct the subject on how to administer the IMP
- Administer the 1st dose of IMP according to randomisation [administration of IMP takes place at the clinic and can be done by either the trial medication delegate or the subject under supervision by the trial medication delegate]:
 - If randomised to FE 999049; starting dose for the first 5 days is fixed at 10 µg or 15 µg according to investigator's assessment
 - If randomised to GONAL-F; starting dose for the first 5 days is fixed at 150 IU or 225 IU according to investigator's assessment
- Dispensing of GnRH agonist, as applicable

The IMP should preferably be administered at the same time each day during the stimulation period and the timing of the IMP administrations should be aligned with the GnRH agonist administrations.

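### The follicle-count models in section 9.6.3 omit the follicle count recorded before randomisation on stimulation day 1, so their intervals may be wider than necessary

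*Combined protocol and SAP*

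**What the plan says.** Section 9.6.3 covers five counts ("Total number of follicles, and number of follicles ≥ 10 mm, ≥ 12 mm, ≥ 15 mm and ≥ 17 mm"), each on stimulation day 6 and at end-of-stimulation, which makes ten analyses. It states that they "will (in separate analyses) be compared between FE 999049 and GONAL-F using the same negative binomial regression model as used for the primary endpoint". Section 9.6.2 defines that model: the comparison is made "using a negative binomial model with treatment and dose level (10 µg/150 IU or 15 µg/225 IU) as factors". There is no baseline covariate.

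The next paragraph of 9.6.3 treats estradiol and progesterone differently. Their models are fitted "with treatment and dose level as factors and with the serum concentration on stimulation day 1 as a covariate", and section 9.6.1 gives a mean-imputation rule for a missing day-1 hormone value used in this way.

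A day-1 follicle count exists. Under the lead-in "The following must take place before randomisation to treatment", section 6.5.1 lists "Transvaginal ultrasound of uterus and ovaries (endometrial thickness, ovarian volume, number and size of follicles". Footnote d of Table 6-1 places the day-1 ultrasound before randomisation as well.

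**The concern.** The count is taken before allocation, so treatment cannot affect it and it is a legitimate covariate. The same section accepts baseline adjustment for one group of secondary endpoints and gives no reason for leaving it out for the other.

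There is some ground in the documents for expecting the count to be prognostic. Section 1.1 lists "markers of ovarian reserve such as antral follicle counts and circulating AMH" among the considerations for choosing a conventional starting dose. Section 3.5.1 reports that the number of oocytes in Trial 000304 was influenced by age and AMH, so ovarian reserve bears on response to this product.

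What is at stake is precision on a secondary endpoint. Follicular development is the first item of the first secondary objective (2.1). If starting follicle number explains part of the later variation within a dose level, leaving it out adds avoidable noise to the estimate.

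**Working it through.** **Inputs from the protocol.** 150 subjects per arm (3.2); SD 7.5, margin 3.00, one-sided 2.5% and 90% power (9.1). The SD is for oocytes. The protocol gives no SD for follicle counts, so 7.5 is used below as an assumed stand-in.

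**Input not in the documents.** r, the correlation of the day-1 count with the later count within dose level. It is an assumption throughout.

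**Step 1: the plan's own figure.** n per arm = 2 × (1.960 + 1.282)² × 7.5² / 3.00² ≈ 131.3, so 132. A t-based calculation gives 133, the stated number. The figure reproduces to within one subject, and nothing here changes it. The protocol states no precision target for the follicle comparisons.

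**Step 2: unadjusted precision.** The 95% half-width is 1.96 × 7.5 × √(2/150) = 1.70 follicles.

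**Step 3: effect of the covariate.** Adjustment multiplies the width by about √(1 − r²).

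| Assumed r | Width factor | Half-width | Narrower by |
|---|---|---|---|
| 0 | 1.000 | 1.70 | 0% |
| 0.1 | 0.995 | 1.69 | 0.5% |
| 0.3 | 0.954 | 1.62 | 4.6% |
| 0.5 | 0.866 | 1.47 | 13.4% |

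**Step 4: does the formula carry over to the planned model?** Negative binomial fits with delta-method differences were simulated (300 subjects, mean about 10, SD about 7.5, 200 runs per setting). Dose level was already in the model and was partly driven by ovarian reserve.

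| Within-stratum r | Adjusted/unadjusted SE, simulated | √(1 − r²) |
|---|---|---|
| 0 | 1.00 | 1.00 |
| 0.15 | 0.99 | 0.99 |
| 0.25 | 0.97 | 0.97 |
| 0.36 | 0.92 | 0.93 |
| 0.45 | 0.87 | 0.89 |

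The formula is a fair guide, and an uninformative covariate costs essentially nothing. The simulated data had log-normal heterogeneity, which is not the gamma form the model assumes, and model SEs ran below the observed spread (0.81 against 0.93 at r = 0). The ratios are therefore the useful output, not the absolute SEs.

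**Step 5: which analyses have a baseline of their own?** Inclusion criterion 13c (4.1.1) excludes follicles of 10 mm or more at confirmation of downregulation. Section 6.5.1 has cysts of 10 mm or more on day 1 punctured, or the subject is ineligible. The day-1 counts for the four size categories are therefore essentially zero. Only the total count, 2 of the 10 analyses, has a like-for-like baseline.

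**The case against.** The strongest reply is that nothing here is an error. Randomisation is stratified by dose level and site (4.2.2), the unadjusted comparison is unbiased, and its interval already allows for chance imbalance in starting follicle number. Follicle counts carry no margin, power claim or success rule. All of that stands.

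The prognostic case is also indirect. The day-1 count follows at least 10 days of GnRH agonist, and the protocol does not call it an antral follicle count. Dose level is the investigator's judgement and already carries some information on reserve. The predictors of response that the protocol reports are age and AMH, for oocytes. This stands too: the gain beyond dose level may be modest or nil. But dose level has only two values, so it need not exhaust the information in the count.

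Using one common model keeps follicles, oocytes, fertilised oocytes and embryos on the same footing. That is a real but small advantage.

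The separate SAP announced in 9.6.1 is not among the documents and may add covariates. This limits certainty; the protocol as written specifies a model without the term.

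A reader might go further in three ways that the documents do not support:

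- **That the follicle intervals are certainly, or much, too wide.** A correlation of 0.7 would make them 29% narrower, but no correlation is given and nothing points to one that high.
- **That all ten analyses ignore a baseline of the same variable.** Step 5 shows otherwise.
- **That day 6 is the cleanest comparison, free of titration and cancellation.** The day-6 ultrasound does precede any dose adjustment. However, the protocol gives day 6 no priority over end-of-stimulation, and cancellation for a safety concern before day 6 is not ruled out (3.1.2).

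**Conclusion.** The point holds as a possible loss of precision on secondary endpoints. A pre-randomisation follicle count is collected and left out of models that sit beside baseline-adjusted hormone models, without a stated reason. There is no bias, and the primary analysis is untouched.

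For assumed r between 0.1 and 0.5 the total-follicle intervals would be about 0.5% to 13% narrower. On the stand-in SD of 7.5, the half-width falls from 1.70 to between 1.69 and 1.47 follicles. If the count predicts nothing beyond dose level, the gain is zero and so, in effect, is the loss from including it. The conclusion rests on r, which the documents do not give, and on the protocol text in the absence of the separate SAP. It is a worthwhile improvement, not a necessary correction.

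**What to change.** - **Section 9.6.3, total follicles (day 6 and end-of-stimulation):** add log(day-1 total follicle count + 1) as a covariate to the negative binomial model, alongside treatment and dose level.
- **Section 9.6.1:** extend the mean-imputation rule for day-1 endocrine covariates to a missing day-1 follicle count, and say on which scale the mean is taken.
- **Absolute difference:** predict each subject's mean under both treatments, average over the observed covariate distribution, take the difference and apply the delta method.
- **Size categories:** the day-1 total count may be used as a general prognostic covariate. This is optional, and the choice should be written down in advance.

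The cost is one model term and some wording in the SAP, with no new data. The follicle model would no longer be identical to the oocyte model, which is a small price. The change should be fixed before unblinding.
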